#### **Power/Sample Size**

We have sufficient power to address our primary aim. Based upon a sample size of n=25 patients per group for this pilot study, we have approximately 70% power to detect a hazard ratio of 2.05 between treatment arms, assuming that only 50% of subjects will experience maturation by six months post randomization in the placebo group. If only 40% of subjects experience maturation by six months post randomization we have over 70% power to detect a hazard ratio of 2.15.

#### **4. Statistical conventions**

This section details general conventions to be used for the statistical analyses and presentation of the data. Departures from these general conventions may be given in the specific detailed sections of this analysis plan.

1. SAS Version 9 or R Version 3 will be the statistical software package used for all data analyses.
2. Continuous variables will be presented with mean, standard deviation, median (25th percentile, 75th percentile), minimum and maximum values. Categorical variables will be presented as number of subjects and percentage of number of subjects by levels of the variable.
3. The number and percentage of responses will be presented in the form XX (XX) where the percentage is in the parentheses. Unless otherwise specified, the denominator for percentages will be the number of subjects in a given treatment group within the analysis population of interest. The denominator will be included when it differs from the standard analysis population.

4. All summary tables will include the analysis population sample size (i.e., number of subjects).
5. Change from baseline will be calculated for each period as follows:  
Change from baseline = Post-baseline value – baseline value.
6. Date variables will be formatted as DD-MON-YYYY for presentation. In the case of missing day, month, and/or year information, “NA” will be presented. For example, a date with a missing month and day will be presented as NANAYYYY.
7. Unless otherwise stated, statistical comparisons will be performed using two-sided significance tests. An alpha level of 0.05 will determine significance unless otherwise noted for a specified analysis.
8. When count data are presented, the percentage will be suppressed when the count is zero in order to draw attention to the non-zero counts.
9. Unless specified otherwise, data will be presented by treatment and control subjects.

## **5. Adverse events data and reporting process**

Adverse events data will be collected at each follow up visit as described above in the section on Study Participants.

The PI will review aggregated AEs each month, and AEs will be reported to the sponsor and the IRB per research guidelines. Participation for the individual will terminate if he/she has a serious adverse reaction that prevents future participation. In the event of adverse effects, the patient's primary physician will be notified.

## Appendix 1: Tables and figures

Table 1. Demographic characteristics of study population

Characteristics	Treatment		Control	
	Left arm N (%)	Right arm N (%)	Left arm N (%)	Right arm N (%)
Age (years) Mean (SD) Median (IQR)				
Site Stanford University Santa Clara Valley				
Male				
Race White Black Asian American Indian Pacific Islander Other Unknown				
Ethnicity Hispanic Non-Hispanic Unknown				
BMI Mean (SD) Median (IQR)				

Table 2. Baseline clinical characteristics of study population

Characteristics	Treatment		Control	
	Left arm N (%)	Right arm N (%)	Left arm N (%)	Right arm N (%)
Had previous surgery				
Ipsilateral tunnel catheter access				
Permanent ipsilateral AV fistula access				
Permanent ipsilateral AV graft access				
Contralateral tunnel catheter access				
Permanent contralateral AV fistula access				
Permanent contralateral AV graft access				
Other surgery type				
Medical history				
None				
Routinely hypotensive				
Diabetes				
Coronary artery disease				
COPD				
Congestive heart failure				
Peripheral artery disease				
Stroke				
Intracranial hemorrhage				
Hypertension				
Cancer				
Peptic ulcer disease				
Other				
Concomitant Medications				
None				
Daily aspirin				
Statins				
Insulin				
Oral diabetic medications				
Antifungal agents				
ACE inhibitors				
ARBs				
Beta blockers				
Calcium channel blockers				
Other antihypertensive				
Diuretics				
Antiarrhythmics				
Other medications				

Table 3. Efficacy and safety outcomes

	Treatment		Control		Hazard ratio (95% CI)
	Left arm N (%)	Right arm N (%)	Left arm N (%)	Right arm N (%)	
Efficacy outcomes					
Time to fistula maturation (days) Mean (SD) Median (IQR)					
AV fistula use within 180 days of surgery					
AV fistula patency at 150- 180 days, with at least 50% increase in vein diameter by ultrasound compared with preoperative vein diameter measurement					
Safety outcomes					Odds ratio (95% CI)
BARC bleeding Type 0 Type 1 Type 2 Type 3a Type 3b Type 3c Type 4 Type 5					
GUSTO bleeding Mild Moderate Severe					

Table 4. Adverse events and other outcomes

	Treatment		Control		Odds ratio (95% CI)
	Left arm N (%)	Right arm N (%)	Left arm N (%)	Right arm N (%)	
Serious adverse events					
Unexpected adverse events					
Other adverse events					
None					
Anemia					
Depression					
Rash					
Iron deficiency					
Retinopathy					
Retinal disorder					
Diplopia/oculomotor disturbances					
Other					
Other outcomes					
Hospitalization					
Unstable angina					
Myocardial infarction					
Cardiac catheterization					
PCI					
CABG					
Non-coronary vascularization					
Stroke					
TIA					
Transfusion					

Figure 1. Kaplan-Meier plot of time to fistula maturation by treatment arm and location of fistula

Figure 2. All outcomes with forest plot for point estimate and 95% confidence interval

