#### **3.4. Statistical Analysis:**

We will derive cumulative incidence plots to depict time to fistula use, stratified by treatment arm and fistula location.

The primary outcome is time to AV fistula maturation, defined as successful cannulation of the AV fistula for six hemodialysis sessions within three weeks.

Subjects who are lost to follow up or who die prior to maturation will be censored at the time of death or last recorded activity.

Our primary analysis will be based on the intention-to-treat principle. To that end, patients will be analyzed according to their randomized treatment assignment, and all patients randomized to treatment assignment will be included in the analysis even if they are lost to follow up or die before the end of their observation period. We will use a log-rank test stratified by location of fistula to assess whether time to maturation of AV fistula differs between treatment arms (vorapaxar versus placebo). The test will be two-sided and conducted at the 0.05 level of significance.

A Cox proportional hazards regression model of treatment arm and other characteristics of interest (if required) will be employed secondarily to estimate an adjusted treatment effect.

Other secondary analyses involve the use of logistic regression techniques to evaluate the effect of treatment on secondary endpoints – use of AV fistula within 180 days, AV fistula patency within 150-180 days and AV fistula functional or anatomic maturation at 180 days as determined by the PI. We will also compare rates of bleeding by treatment arm using t-tests or Wilcoxon rank sum tests as appropriate.

**UPDATED: Based on low enrollment and early termination of the study, the planned analysis as described above will not be conducted. Instead, we will conduct a descriptive analysis only.**

**UPDATED: The secondary outcome “AV fistula functional or anatomic maturation at 180 days as determined by the PI” will be defined using clinically adjudicated after a review of the medical record.**

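### SAP Table 3 summarises the time-to-event primary outcome with an ordinary mean (SD) and median (IQR), although the plan assumes only 50% (alternatively 40%) mature by six months

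*SAP*

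**What the plan says.** - SAP Appendix 1, Table 3, lists the primary outcome as "Time to fistula maturation (days) Mean (SD) Median (IQR". Table 1 uses the same layout for age and BMI.
- SAP 4, item 2, sets the general format: "Continuous variables will be presented with mean, standard deviation, median (25th percentile, 75th percentile), minimum and maximum values". The preamble adds "Departures from these general conventions may be given in the specific detailed sections of this analysis plan", but neither SAP 3.4 nor Table 3 gives a departure for this row.
- SAP 2.3 defines the outcome as a time to event. SAP 3.4 says "Subjects who are lost to follow up or who die prior to maturation will be censored" and, under intention to treat, "all patients randomized to treatment assignment will be included in the analysis".
- The power section works from "assuming that only 50% of subjects will experience maturation by six months post randomization in the placebo group", with an alternative: "If only 40% of subjects experience maturation by six months post randomization".
- The update in SAP 3.4 withdraws the planned tests and models: "Instead, we will conduct a descriptive analysis only". Figure 1 in the appendix is a Kaplan-Meier plot of the same outcome.

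**The concern.** A sample mean, SD and IQR need a value for every patient. On the plan's own assumption, 50% to 60% of placebo patients have no maturation time at six months. Someone filling in the shell must either leave them out or give them a follow-up time in place of a maturation time, and the row does not say which.

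Leaving them out is the damaging choice. It selects patients on the outcome, and it selects differently in the two groups if the drug works: a drug that brings slower fistulas to maturation adds long times to its own average. The group in which more fistulas mature can then show the longer mean time. With the log-rank test and Cox model withdrawn, there is no planned comparative estimate beside the row to correct that impression.

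**Working it through.** **Inputs.** SAP power section: 25 per group; placebo proportion matured by six months p = 0.50 with hazard ratio (HR) 2.05 (case 1), or p = 0.40 with HR 2.15 (case 2). The 40% sentence does not repeat that it means placebo; I read it so. Assumptions of mine: D = 182.6 days for six months, exponential times, proportional hazards, everyone followed to D, groups pooled over left and right arm.

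**The plan's own figures.** Unmatured on placebo: 1 - 0.50 = 50% (12.5 of 25) and 1 - 0.40 = 60% (15 of 25). The power quoted beside them does not reproduce. In case 1, events = 25 × (0.500 + 0.759) = 31.5, and Schoenfeld's formula gives about 52% two-sided, not about 70%; case 2 gives about 51%. That is a separate matter, and nothing below depends on it.

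**Can the placebo median and IQR be observed?** With 25 patients and no dropout, the median needs at least 13 matured and the upper quartile at least 19. Binomial probabilities: 50% and 0.7% in case 1; 15% and 0.03% in case 2. An IQR for all placebo patients would almost never be available.

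**Matured-only mean against restricted mean.** λ0 = -ln(1 - p)/D, λ1 = HR × λ0, F = 1 - exp(-λD).
- Matured-only mean = 1/λ - D·exp(-λD)/F. Case 1 placebo: 263.4 - 182.6 × 0.5/0.5 = 80.8 days.
- Restricted mean to D = F/λ. Case 1 placebo: 0.5 × 263.4 = 131.7 days.

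| | Placebo | Vorapaxar | Difference (days) |
|---|---|---|---|
| Case 1, F | 0.500 | 0.759 | |
| Case 1, matured-only mean | 80.8 | 70.4 | about 10 |
| Case 1, restricted mean | 131.7 | 97.5 | about 34 |
| Case 2, F | 0.400 | 0.667 | |
| Case 2, matured-only mean | 83.6 | 74.9 | about 9 |
| Case 2, restricted mean | 143.0 | 110.8 | about 32 |

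**Other shapes.** With Weibull shape 0.7 to 3, no maturation before 0 to 6 weeks, and six-month proportions held fixed, the matured-only difference is 4.5 to 10.5 days and the restricted-mean difference 13 to 38 days, always 2.6 to 4.2 times larger.

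**Direction of the difference.** The documents do not give the enrolment reached, so I simulated a range (200,000 trials per size). Share of trials in which the mean is longer on vorapaxar:

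| Patients per group | 5 | 10 | 15 | 25 |
|---|---|---|---|---|
| Case 1, matured-only | 41% | 37% | 34% | 29% |
| Case 1, restricted | 20% | 12% | 7% | 3% |
| Case 2, matured-only | 44% | 40% | 38% | 34% |
| Case 2, restricted | 21% | 13% | 8% | 4% |

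Trials with no matured patient in a group are left out of the matured-only rows (3.2% and 8.2% at n = 5, under 1% from n = 10). In 28-34% of trials, across sizes and cases, more patients mature on vorapaxar yet its matured-only mean is longer.

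**Unmatured patients entered at their last day.** With full follow-up this equals the restricted mean above. With final visits spread evenly over the ±4-week window of Protocol 2.4, it is about 131 v 97 days in case 1 and 143 v 111 in case 2, almost unchanged.

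**The case against.** The strongest reply is that the row is undefined rather than wrong. The SAP nowhere says that matured patients alone are to be averaged. Its median can be read as a Kaplan-Meier median, SAP 3.2 promises a description of missing data for each variable, and SAP 4 item 4 requires the sample size in every summary table. These make a silent matured-only mean less likely. They do not say what the mean and SD are, and SAP 4 item 2, followed literally, gives the ordinary ones.

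Several stronger readings are tempting, and the documents do not support them.
- *Any mean in this row misleads.* Entering unmatured patients at their last day gives nearly the restricted mean. It moves materially only if final visits cluster at one end of the window: case 1 would give 117 v 90 days if all fell at day 155, and 145 v 104 if all fell at day 211. SAP 3.2 expects only one or two patients with incomplete visits. The fault there is the label.
- *Patients alive and unmatured have no rule.* The censoring sentence does not name them, but the log-rank test, Cox model and Figure 1 all imply censoring at the end of follow-up. One clarifying sentence is missing, not a method.
- *The bias has a known size.* The hazard ratios are detectable effects in a power statement. The plan forecasts no vorapaxar maturation rate; 76% and 67% are derived here.
- *This row is the trial's main result.* The update does not say which shells survive, and Table 3 lacks the secondary outcome added in 2018, so it was evidently not revised.
- *The hazard-ratio heading over binary outcomes adds to the problem.* The models behind it are withdrawn, so that point is moot.

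**Conclusion.** The point holds as a fault in how the primary outcome is summarised. An ordinary mean (SD) and median (IQR) do not suit an outcome that half or more of the placebo patients are assumed not to reach during follow-up. The harm shown belongs to the matured-only reading: it would show roughly 30% of the restricted-mean difference (10 of 34 days, or 9 of 32) and would favour the wrong group in about 29-44% of trials.

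Those sizes rest on exponential times, proportional hazards at the design hazard ratios, complete follow-up and 5 to 25 patients per group. The mismatch between the summary and the outcome needs only the plan's maturation assumption. Severity is minor to moderate: no test or decision hangs on the row, and Figure 1 and the row for use within 180 days remain.

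**What to change.** Replace the Table 3 row, by treatment group with a total column for each group, by:
- number matured, number censored and number who died unmatured;
- Kaplan-Meier median and quartiles, printed as 'not reached' where that applies;
- cumulative proportion matured by day 180 with 95% CI, treating death before maturation as a competing event, or stating that deaths are censored. The choice should be explicit: SAP 3.4 censors deaths, the SAP background puts dialysis mortality near one in five a year, and one minus Kaplan-Meier with deaths censored overstates the proportion who mature.

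Label any mean that is kept either 'restricted mean to day 180' or 'matured patients only'. In SAP 4 item 2, exempt time-to-event variables. In SAP 3.4, state that patients alive and unmatured are censored at the end of follow-up, as Figure 1 already implies.

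The cost is a revised table shell and a few sentences of SAP text. No new data are needed, and the Kaplan-Meier estimate is already required for Figure 1.

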### **1.3. Hypotheses**

1. Vorapaxar initiated two days following AV fistula creation will result in improved fistula functional maturation without increased risk of bleeding or other major adverse events.
2. Vorapaxar initiated two days following AV fistula creation will result in improved fistula patency and will increase the utility of secondary procedures to aid in fistula maturation, without increased risk of bleeding or other major adverse events.
3. Vorapaxar initiated two days following AV fistula creation will facilitate successful cannulation of AV fistulas for hemodialysis without increased risk of bleeding or other major adverse events.

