## **2. Study Design**

### **2.1. Study Design**

This is a randomized placebo-controlled double-blind pilot trial. Half of enrolled patients will receive the study drug (vorapaxar [Zontivity™] 2.5 mg daily) and half will receive a look-alike placebo.

Patients will be assigned to treatment groups with a 1:1 randomization in blocks of 4 at the conclusion of the AV fistula creation. Patients will be stratified based on fistula location (lower arm versus upper arm). Randomization will be performed after successful creation of an arteriovenous fistula, on the day of surgery. We expect to randomize 50 patients.

The study drug (12-week supply of study drug or placebo) will be dispensed to enrolled patients on the day of surgery. Participants will be instructed to start taking their study medications on Day-two post-surgery.

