### 2.3. Study Endpoints

The primary efficacy outcome is time to AV fistula functional maturation (defined as successful cannulation of the AV fistula for six hemodialysis sessions within three weeks).

The secondary efficacy outcomes are:

- AV fistula use within 180 days of surgery
- AV fistula patency at 150-180 days, with at least 50% increase in vein diameter by ultrasound compared with preoperative vein diameter measurement
- Update: New secondary outcome added: AV fistula functional or anatomic maturation at 180 days as determined by the PI

The safety outcomes are bleeding events as determined by BARC and GUSTO criteria.

BARC Bleeding Classification

- Type 0: No bleeding

- Type 1: Bleeding that is not actionable and does not cause the patient to seek unscheduled performance of studies, hospitalization, or treatment by a healthcare professional; may include episodes leading to self-discontinuation of medical therapy by the patient without consulting a healthcare professional
- Type 2: Any overt, actionable sign of hemorrhage (e.g., more bleeding than would be expected for a clinical circumstance, including bleeding found by imaging alone) that does not fit the criteria for type 3, 4, or 5 but does meet at least one of the following criteria: (1) requiring nonsurgical, medical intervention by a healthcare professional, (2) leading to hospitalization or increased level of care, or (3) prompting evaluation
- Type 3
  - Type 3a: Overt bleeding plus hemoglobin drop of 3 to 5 g/dL\* (provided hemoglobin drop is related to bleed) Any transfusion with overt bleeding
  - Type 3b: Overt bleeding plus hemoglobin drop >5 g/dL\* (provided hemoglobin drop is related to bleed); Cardiac tamponade; Bleeding requiring surgical intervention for control (excluding dental/nasal/skin/hemorrhoid); Bleeding requiring intravenous vasoactive agents
  - Type 3c: Intracranial hemorrhage (does not include micro-bleeds or hemorrhagic transformation, does include intraspinal); Subcategories confirmed by autopsy or imaging or lumbar puncture; Intraocular bleed compromising vision
- Type 4 CABG bleeding
- Type 5: Fatal bleeding

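### SAP Table 3 and Figure 2 still ask for odds ratios for bleeding, apparently one per BARC and GUSTO level, although the analysis is now descriptive only; many of these ratios are likely to be zero, infinite or 0/0

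*SAP*

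**What the plan says.** SAP 2.3 defines the safety endpoint in one sentence: "The safety outcomes are bleeding events as determined by BARC and GUSTO criteria". Each hypothesis in SAP 1.3 carries the rider "without increased risk of bleeding or other major adverse events".

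The display is set out in SAP Appendix 1. The safety block of Table 3 lists "BARC bleeding Type 0 Type 1 Type 2 Type 3a Type 3b Type 3c Type 4 Type 5", followed by GUSTO mild, moderate and severe, and its effect column is headed as an odds ratio with 95% CI. Figure 2 is a forest plot giving a point estimate and 95% CI for all outcomes.

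The text of SAP 3.4 does not lead to those ratios. It assigns logistic regression to the secondary efficacy endpoints only. For bleeding it says "We will also compare rates of bleeding by treatment arm using t-tests or Wilcoxon rank sum tests as appropriate". The same section was then updated: "Based on low enrollment and early termination of the study, the planned analysis as described above will not be conducted". It continues: "Instead, we will conduct a descriptive analysis only".

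Neither document gives a bleeding rate, a pooled bleeding category, a rule for combining a patient's bleeds across visits, or a rule for zero cells. Section 4 of the SAP, item 8, suppresses the percentage when a count is zero.

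**The concern.** Under a descriptive-only analysis, the counts and estimates that are tabulated are what a reader has to judge bleeding by. Two features of the shell work against that.

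First, the severity levels are finely divided and the trial is small. Where a level is empty in one treatment group, the sample odds ratio is zero or infinite; where it is empty in both, it is 0/0. With the percentage suppressed as well, such a row would show neither a rate nor a two-sided estimate.

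Second, a ratio for a single level of an ordered scale can point the wrong way. If treatment makes bleeds more severe without changing how many patients bleed, patients leave Type 1 for a higher type and the Type 1 ratio falls below one.

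At stake is how clearly the report shows what increase in bleeding the data are compatible with, which is the safety half of every hypothesis.

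**Working it through.** **Inputs from the documents.** Planned size, SAP Power/Sample Size: "Based upon a sample size of n=25 patients per group for this pilot study". Allocation, SAP 2.1: "1:1 randomization in blocks of 4". Table 3 lists 8 BARC types and 3 GUSTO grades, 11 levels in all. There is no stated bleeding figure to reproduce.

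**Assumed inputs.** The true risk of a level, taken as equal in both groups, and the enrolment reached. The SAP says only that enrolment was low, so 10, 12 and 6 per group are illustrations.

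**1. Chance that a level is empty in at least one group.** With n per group and risk p, one group is empty with probability (1−p)^n, so P = 1 − [1 − (1−p)^n]².

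| n per group | p = 2% | p = 4% | p = 8% |
|---|---|---|---|
| 25 | 84% | 59% | 23% |
| 10 (assumed) | 97% | 89% | 68% |

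Example: 0.98^25 = 0.6035, and 1 − (1 − 0.6035)² = 0.843. At 25 per group the chance passes 50% once p is below about 4.8%. At 12 per group the threshold is about 9.7%. For a common level the problem disappears: at p = 15% and 25 per group the chance is about 3%.

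**2. Expected number of the 11 levels affected.** This needs assumed distributions.

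| Any bleeding | BARC 0, 1, 2, 3a, 3b, 3c, 4, 5 (%) | GUSTO mild, moderate, severe (%) |
|---|---|---|
| 15% | 85, 8, 4, 1.5, 1, 0.25, 0, 0.25 | 12, 2, 1 |
| 30% | 70, 15, 8, 3.5, 2, 0.5, 0, 1 | 22, 5, 3 |
| 50% | 50, 22, 14, 7, 4, 1, 0, 2 | 35, 9, 6 |

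Here a group in which every patient has the level also counts, so the per-level chance is 1 − [1 − (1−p)^n − p^n]². The 0/0 chance is (1−p)^(2n). Summing over the 11 levels, for any-bleeding rates of 15% / 30% / 50%:

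| n per group | No finite non-zero ratio | Of these, 0/0 |
|---|---|---|
| 25 | 7.6 / 5.9 / 4.3 | 5.0 / 3.2 / 2.2 |
| 12 | 9.0 / 7.5 / 6.1 | 6.3 / 4.6 / 3.3 |
| 6 | 10.1 / 8.9 / 7.8 | 7.5 / 6.1 / 4.7 |

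**3. Precision where a ratio exists.** Wald intervals: 4/25 v 2/25 gives 2.19 (0.36 to 13.2), and 2/25 v 1/25 gives 2.09 (0.18 to 24.6).

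**4. Direction.** Suppose 4/25 in each group would have a Type 1 bleed, and treatment moves two of its four to a higher type. The Type 1 odds ratio becomes (2×21)/(4×23) = 0.46. The number of patients who bleed is unchanged, yet the row looks protective.

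**5. Does the alternative work at zero counts?**
- The exact 95% upper limit for 0/n is 1 − 0.025^(1/n): 13.7% for 0/25 and 30.8% for 0/10.
- The Newcombe score interval for a risk difference is also defined. The Wilson limit for 0/25 is 1.96²/(25 + 1.96²) = 13.3%, so 0/25 v 0/25 gives a difference of 0 (−13.3 to +13.3 percentage points).
- For 3/25 v 0/25 the Wilson intervals are 4.2% to 30.0% and 0 to 13.3%. The difference is 12 points, from 12 − √(7.8² + 13.3²) = −3.5 to 30.0.

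**6. Would odds ratios on pooled thresholds be enough?** Not reliably. For BARC 3 or higher at an assumed 3% to 14%, the chance of an empty group is 72% to 4.6% with 25 per group and 91% to 30% with 12. The risk difference is therefore preferable for the severe thresholds.

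**The case against.** The update in SAP 3.4 cancels the planned analysis, and the shells may simply be leftovers: Table 3 also lacks the secondary outcome added in 2018. This largely stands. It makes the point one of reconciling the shells with the text. It does not remove the point, because the update refers to the analysis described above it, while the table and figure that follow still call for ratios and intervals.

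Several stronger readings are tempting, and the documents do not support them.

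- **That odds ratios and t-tests are in live conflict for the same outcome.** The sentence in question names t-tests or Wilcoxon tests and belongs to the cancelled analysis. A rank test on the ordered grade would in any case have used the whole scale.
- **That most of the ratios will be undefined.** This depends on bleeding rates the documents do not give. At 25 per group and 50% any bleeding, 4.3 of 11 levels lack a finite non-zero ratio. In the strict 0/0 sense the affected levels are a minority at 25 per group in all three scenarios.
- **That a zero cell leaves no interval at all.** Conditional exact bounds exist: 3/25 v 0/25 gives 0.42 to infinity, and 0/25 v 2/25 gives 0 to 5.3. The SAP names no such method, however, and a 0/0 row carries no information about the ratio.
- **That one ratio per level is certain.** The levels appear in one table cell as extracted, so one ratio per scale cannot be excluded. The SAP would then have to say what that ratio compares.
- **That the display hides the data.** Table 3 does have N (%) columns, and a reader could derive limits from the counts and add up levels, provided each patient is counted once. The SAP does not say so.

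Finally, wide intervals reflect a small trial, and no display cures that.

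**Conclusion.** The point holds as an inexpensive improvement to the safety display. Table 3 and Figure 2 were not brought into line with the descriptive-only update, and no text says how their bleeding ratios would be obtained or what happens with zero cells.

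The size depends on assumed risks. For a level with a true risk of 2% to 8%, the chance of an empty treatment group is 84% to 23% at the planned 25 per group, and 97% to 68% at an assumed 10. It is fair to say that many level-specific ratios are likely to be zero, infinite or 0/0, and more of them at reduced enrolment. A reader might infer that most are certain to fail, or that the trial cannot report on bleeding; neither follows.

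The Type 1 distortion needs no assumption about the overall bleeding rate, only that some patients move from Type 1 to a higher type. All of this rests on the natural reading of one ratio per level.

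**What to change.** In SAP Table 3:

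1. State that each patient is counted once on each scale, by the worst bleed over follow-up.
2. Keep the individual BARC types and GUSTO grades as counts, without ratios.
3. Add cumulative rows: any bleeding; BARC 2 or higher; BARC 3 or higher; GUSTO moderate or severe. State how Type 4 (CABG bleeding) is counted.
4. For those rows give n/N per randomised group with an exact 95% CI, and the risk difference with an exact or score 95% CI, naming the method. The shell splits each treatment into left-arm and right-arm columns, so a total per treatment is needed.
5. Show the percentage and interval for these rows even when the count is zero, as an exception to item 8 of SAP Section 4.

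In Figure 2, plot the bleeding risk differences for the same rows. The t-test/Wilcoxon sentence is already superseded and needs no separate action.

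The cost is a small edit to the table and figure shells, with no new data. The downside is that the intervals will look wide, which is an accurate picture of what a trial of this size can say.
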